**APPENDIX IV: TRIAL FLOW DIAGRAM. adapted from CONSORT guidelines, 2010^24**

Protocol #: 1

---

## **APPENDIX V: WORLD MEDICAL ASSOCIATION DECLARATION OF HELSINKI, ETHICAL PRINCIPLES FOR MEDICAL RESEARCH INVOLVING HUMAN SUBJECTS**

Adopted by the 18th WMA General Assembly, Helsinki, Finland, June 1964  
and amended by the:

29th WMA General Assembly, Tokyo, Japan, October 1975

35th WMA General Assembly, Venice, Italy, October 1983

41st WMA General Assembly, Hong Kong, September 1989

48th WMA General Assembly, Somerset West, Republic of South Africa, October 1996

52nd WMA General Assembly, Edinburgh, Scotland, October 2000

53rd WMA General Assembly, Washington DC, USA, October 2002 (Note of Clarification added)

55th WMA General Assembly, Tokyo, Japan, October 2004 (Note of Clarification added)

59th WMA General Assembly, Seoul, Republic of Korea, October 2008

64th WMA General Assembly, Fortaleza, Brazil, October 2013

### **Preamble**

1. The World Medical Association (WMA) has developed the Declaration of Helsinki as a statement of ethical principles for medical research involving human subjects, including research on identifiable human material and data.

The Declaration is intended to be read as a whole and each of its constituent paragraphs should be applied with consideration of all other relevant paragraphs.

2. Consistent with the mandate of the WMA, the Declaration is addressed primarily to physicians. The WMA encourages others who are involved in medical research involving human subjects to adopt these principles.

### **General Principles**

3. The Declaration of Geneva of the WMA binds the physician with the words, "The health of my patient will be my first consideration," and the International Code of Medical Ethics declares that, "A physician shall act in the patient's best interest when providing medical care."

4. It is the duty of the physician to promote and safeguard the health, well-being and rights of patients, including those who are involved in medical research. The physician's knowledge and conscience are dedicated to the fulfilment of this duty.

5. Medical progress is based on research that ultimately must include studies involving human subjects.

6. The primary purpose of medical research involving human subjects is to understand the causes, development and effects of diseases and improve preventive, diagnostic and therapeutic interventions (methods, procedures and treatments). Even the best proven interventions must be evaluated continually through research for their safety, effectiveness, efficiency, accessibility and quality.

7. Medical research is subject to ethical standards that promote and ensure respect for all human subjects and protect their health and rights.

Protocol #: 1

---

8. While the primary purpose of medical research is to generate new knowledge, this goal can never take precedence over the rights and interests of individual research subjects.
9. It is the duty of physicians who are involved in medical research to protect the life, health, dignity, integrity, right to self-determination, privacy, and confidentiality of personal information of research subjects. The responsibility for the protection of research subjects must always rest with the physician or other health care professionals and never with the research subjects, even though they have given consent.
10. Physicians must consider the ethical, legal and regulatory norms and standards for research involving human subjects in their own countries as well as applicable international norms and standards. No national or international ethical, legal or regulatory requirement should reduce or eliminate any of the protections for research subjects set forth in this Declaration.
11. Medical research should be conducted in a manner that minimises possible harm to the environment.
12. Medical research involving human subjects must be conducted only by individuals with the appropriate ethics and scientific education, training and qualifications. Research on patients or healthy volunteers requires the supervision of a competent and appropriately qualified physician or other health care professional.
13. Groups that are underrepresented in medical research should be provided appropriate access to participation in research.
14. Physicians who combine medical research with medical care should involve their patients in research only to the extent that this is justified by its potential preventive, diagnostic or therapeutic value and if the physician has good reason to believe that participation in the research study will not adversely affect the health of the patients who serve as research subjects.
15. Appropriate compensation and treatment for subjects who are harmed as a result of participating in research must be ensured.

**Risks, Burdens and Benefits**

16. In medical practice and in medical research, most interventions involve risks and burdens. Medical research involving human subjects may only be conducted if the importance of the objective outweighs the risks and burdens to the research subjects.
17. All medical research involving human subjects must be preceded by careful assessment of predictable risks and burdens to the individuals and groups involved in the research in comparison with foreseeable benefits to them and to other individuals or groups affected by the condition under investigation. Measures to minimise the risks must be implemented. The risks must be continuously monitored, assessed and documented by the researcher.
18. Physicians may not be involved in a research study involving human subjects unless they are confident that the risks have been adequately assessed and can be satisfactorily managed.

When the risks are found to outweigh the potential benefits or when there is conclusive proof of definitive outcomes, physicians must assess whether to continue, modify or immediately stop the study.

**Vulnerable Groups and Individuals**

Protocol #: 1

---

19. Some groups and individuals are particularly vulnerable and may have an increased likelihood of being wronged or of incurring additional harm.

All vulnerable groups and individuals should receive specifically considered protection.

20. Medical research with a vulnerable group is only justified if the research is responsive to the health needs or priorities of this group and the research cannot be carried out in a non-vulnerable group. In addition, this group should stand to benefit from the knowledge, practices or interventions that result from the research.

**Scientific Requirements and Research Protocols**

21. Medical research involving human subjects must conform to generally accepted scientific principles, be based on a thorough knowledge of the scientific literature, other relevant sources of information, and adequate laboratory and, as appropriate, animal experimentation. The welfare of animals used for research must be respected.

22. The design and performance of each research study involving human subjects must be clearly described and justified in a research protocol.

The protocol should contain a statement of the ethical considerations involved and should indicate how the principles in this Declaration have been addressed. The protocol should include information regarding funding, sponsors, institutional affiliations, potential conflicts of interest, incentives for subjects and information regarding provisions for treating and/or compensating subjects who are harmed as a consequence of participation in the research study.

In clinical trials, the protocol must also describe appropriate arrangements for post-trial provisions.

**Research Ethics Committees**

23. The research protocol must be submitted for consideration, comment, guidance and approval to the concerned research ethics committee before the study begins. This committee must be transparent in its functioning, must be independent of the researcher, the sponsor and any other undue influence and must be duly qualified. It must take into consideration the laws and regulations of the country or countries in which the research is to be performed as well as applicable international norms and standards but these must not be allowed to reduce or eliminate any of the protections for research subjects set forth in this Declaration.

The committee must have the right to monitor ongoing studies. The researcher must provide monitoring information to the committee, especially information about any serious adverse events. No amendment to the protocol may be made without consideration and approval by the committee. After the end of the study, the researchers must submit a final report to the committee containing a summary of the study's findings and conclusions.

**Privacy and Confidentiality**

24. Every precaution must be taken to protect the privacy of research subjects and the confidentiality of their personal information.

Protocol #: 1

---

### **Informed Consent**

25. Participation by individuals capable of giving informed consent as subjects in medical research must be voluntary. Although it may be appropriate to consult family members or community leaders, no individual capable of giving informed consent may be enrolled in a research study unless he or she freely agrees.

26. In medical research involving human subjects capable of giving informed consent, each potential subject must be adequately informed of the aims, methods, sources of funding, any possible conflicts of interest, institutional affiliations of the researcher, the anticipated benefits and potential risks of the study and the discomfort it may entail, post-study provisions and any other relevant aspects of the study. The potential subject must be informed of the right to refuse to participate in the study or to withdraw consent to participate at any time without reprisal. Special attention should be given to the specific information needs of individual potential subjects as well as to the methods used to deliver the information.

After ensuring that the potential subject has understood the information, the physician or another appropriately qualified individual must then seek the potential subject's freely-given informed consent, preferably in writing. If the consent cannot be expressed in writing, the non-written consent must be formally documented and witnessed.

All medical research subjects should be given the option of being informed about the general outcome and results of the study.

27. When seeking informed consent for participation in a research study the physician must be particularly cautious if the potential subject is in a dependent relationship with the physician or may consent under duress. In such situations the informed consent must be sought by an appropriately qualified individual who is completely independent of this relationship.

28. For a potential research subject who is incapable of giving informed consent, the physician must seek informed consent from the legally authorised representative. These individuals must not be included in a research study that has no likelihood of benefit for them unless it is intended to promote the health of the group represented by the potential subject, the research cannot instead be performed with persons capable of providing informed consent, and the research entails only minimal risk and minimal burden.

29. When a potential research subject who is deemed incapable of giving informed consent is able to give assent to decisions about participation in research, the physician must seek that assent in addition to the consent of the legally authorised representative. The potential subject's dissent should be respected.

30. Research involving subjects who are physically or mentally incapable of giving consent, for example, unconscious patients, may be done only if the physical or mental condition that prevents giving informed consent is a necessary characteristic of the research group. In such circumstances the physician must seek informed consent from the legally authorised representative. If no such representative is available and if the research cannot be delayed, the study may proceed without informed consent provided that the specific reasons for involving subjects with a condition that renders them unable to give informed consent have been stated in the research protocol and the study has been approved by a research ethics committee. Consent to remain in the research must be obtained as soon as possible from the subject or a legally authorised representative.

Protocol #: 1

---

31. The physician must fully inform the patient which aspects of their care are related to the research. The refusal of a patient to participate in a study or the patient's decision to withdraw from the study must never adversely affect the patient-physician relationship.

32. For medical research using identifiable human material or data, such as research on material or data contained in biobanks or similar repositories, physicians must seek informed consent for its collection, storage and/or reuse. There may be exceptional situations where consent would be impossible or impracticable to obtain for such research. In such situations the research may be done only after consideration and approval of a research ethics committee.

**Use of Placebo**

33. The benefits, risks, burdens and effectiveness of a new intervention must be tested against those of the best proven intervention(s), except in the following circumstances:

Where no proven intervention exists, the use of placebo, or no intervention, is acceptable; or

Where for compelling and scientifically sound methodological reasons the use of any intervention less effective than the best proven one, the use of placebo, or no intervention is necessary to determine the efficacy or safety of an intervention and the patients who receive any intervention less effective than the best proven one, placebo, or no intervention will not be subject to additional risks of serious or irreversible harm as a result of not receiving the best proven intervention. Extreme care must be taken to avoid abuse of this option.

**Post-Trial Provisions**

34. In advance of a clinical trial, sponsors, researchers and host country governments should make provisions for post-trial access for all participants who still need an intervention identified as beneficial in the trial. This information must also be disclosed to participants during the informed consent process.

**Research Registration and Publication and Dissemination of Results**

35. Every research study involving human subjects must be registered in a publicly accessible database before recruitment of the first subject.

36. Researchers, authors, sponsors, editors and publishers all have ethical obligations with regard to the publication and dissemination of the results of research. Researchers have a duty to make publicly available the results of their research on human subjects and are accountable for the completeness and accuracy of their reports. All parties should adhere to accepted guidelines for ethical reporting. Negative and inconclusive as well as positive results must be published or otherwise made publicly available. Sources of funding, institutional affiliations and conflicts of interest must be declared in the publication. Reports of research not in accordance with the principles of this Declaration should not be accepted for publication.

**Unproven Interventions in Clinical Practice**

37. In the treatment of an individual patient, where proven interventions do not exist or other known interventions have been ineffective, the physician, after seeking expert advice, with informed consent from the patient or a legally authorised representative, may use an unproven intervention if in the physician's judgement it offers hope of saving life, re-establishing health or alleviating suffering. This intervention should subsequently be made the object of research, designed to evaluate its safety and efficacy. In all cases, new information must be recorded and, where appropriate, made publicly available.

## 2. Introduction

### 2.1. Background / rationale

Neonatal mortality remains unacceptably high and complications of prematurity are the most common, direct, cause of death in children aged under 5y. Nearly half of all preterm neonates die within the first 24h after birth, before post-natal stabilisation has occurred. Focusing on improving hospital care for preterm neonates in the early neonatal period is a global research and public health priority if global neonatal mortality reduction targets are to be met.

Kangaroo mother care (KMC) is recommended as standard care for all hospitalised babies <2000g who are fully stable and have completed the post-natal stabilisation process. It was developed in Colombia in 1978 and has since been adopted in both high-income (HIC) and low-middle income countries (LMIC) as an adjunct to incubator care. KMC is a package of care with the key component being prolonged, continuous skin-to-skin contact between the nearly naked baby and mother/caregiver. This leads to promotion of early and exclusive breastfeeding and early discharge from hospital. There is strong evidence of mortality (36 – 51% reduction) and clinical benefits (reduced nosocomial infection, improved growth, and stability) for KMC in stabilised preterm neonates. However, there is an evidence gap for KMC in neonates who have not completed stabilisation and this is a potentially feasible, game changing intervention for health facility care of the small and sick neonate. There is also an evidence gap with respect to our understanding of how KMC reduces nosocomial and severe infections.

### 2.2. Hypothesis

Using early continuous skin-to-skin contact in pre-stabilised preterm neonates will improve survival by:

1. Early onset, early impact, stabilisation pathways which improve thermal control and promote cardio-respiratory stabilisation
2. Early onset, late impact causal pathways, including prevention of late-onset infections, gastro-intestinal stability and prevention of apnoea of prematurity.

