**Outcomes**

All-cause mortality: Death of a neonate due to any reason within a defined time period

Suspected late onset infection: New onset of any 1 of the following at > 72h of age:  
Pallor; Lethargy; Jaundice; Apnoea; Hepatomegaly

Confirmed late onset infection: New onset of any 1 of the following at > 72h of age:  
Pallor; Lethargy; Jaundice; Apnoea; Hepatomegaly  
AND blood or CSF culture positive for known neonatal pathogen

Hypoglycaemia: Blood sugar level < 2.6 mmol/l, as measured by bedside testing

Hypothermia: Auxillary temperature less than the normal range (36.5°C – 37.5 °C)

Mild hypothermia: 36.0 °C – 36.4 °C

Moderate hypothermia: 32.0 °C – 35.9 °C

Severe hypothermia: <32.0 °C

Hypothermia density: Proportion of time temperature <36.5 °C during a defined time period

Duration of admission: Time from hospital admission to discharge

Protocol #: 1

---

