## 1.2 Rationale

Neonatal mortality remains unacceptably high and complications of prematurity are the most common, direct, cause of death in children aged under 5y. Feasible hospital based interventions to reduce mortality in resource limited settings are urgently needed.

The hospital management of preterm/LBW babies is challenging in resource limited settings, for multiple reasons, including: lack of essential newborn care and supportive management; high patient: health care worker ratios and increased risk of hospital acquired infections. Investigation and development of feasible, low cost strategies for the management of these babies within the critical early neonatal period is a global research and public health priority.

Kangaroo mother care is an evidence based and safe intervention currently used for stable newborns <2000g with significant mortality effect. Early, continuous skin-to-skin contact used in unstable newborns has the potential to improve survival through a combination of early and late mechanistic pathways, of which thermal control, cardio-respiratory stability and infection prevention control are the most important.

It is hypothesised that early continuous skin-to-skin contact in mild-moderately unstable neonates will improve survival by:

1. *Early onset, early* impact, stabilisation pathways which improve thermal control, promote cardio-respiratory stabilisation and modulate the natural history of preterm complications.
2. *Early onset, late* impact, pathways include prevention of late-onset infection, promotion of gastro-intestinal stability through improved breast milk feeding and improved recognition of apnoeic events needing resuscitation.

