#### **6.1.3 Evaluations in event of clinical deterioration**

Study site staff will be given guidance and training on recognition of signs of severe illness according to adapted PSBI criteria (figure 3) and asked to inform research personnel if a baby fulfils the screening criteria. Research personnel (research nurses or clinician) will then examine the baby as soon as possible, for the presence of any signs of infection (figure 4). The participant will also be assessed for signs of severe illness and infection during the daily in-patient review. If the subject meets criteria for suspected late-onset infection they will have blood +/- CSF cultures taken as soon as possible but not to delay antibiotic administration (section 5.3.2). Once samples have been taken, management will be directed by the study site team in accordance with the standardised management protocol and the research clinician will complete the appropriate safety monitoring documentation. The study personnel will also assess if the baby meets criteria for temporary withdrawal from the intervention arm.

Figure 3. Screening criteria for severe illness

Hospital staff to inform study team as soon as possible if any of the following are present:

(adapted PSBI criteria)

- Refusal to feed / abdominal distension or pre-feed gastric aspirates > 50% of feed volume
- Lethargic (not moving or moving with stimulation only)
- Respiratory rate >80 bpm or severe chest wall indrawing or new oxygen/CPAP requirement
- Apnoea\*
- Auxillary temp >37.5
- Auxillary temp <35.5 (after 1h of observed skin-to-skin contact)
- Convulsions

Figure 4. Criteria for investigation of suspected late-onset infection

Take blood +/- CSF culture if clinical deterioration at  $\geq 72$ h of age and has 1 of:

- Jaundice
- Apnoea\*
- Hepatomegaly
- Pallor
- Lethargy or movement only when stimulated

Protocol #: 1

---

\*Spontaneous apnoea with no identifiable reason. (E.g. not associated with milk aspiration, severe respiratory distress or end stage respiratory failure)

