#### *Additional analysis*

Logistical regression will be used to explore risk factors for the following outcomes: mortality at 28d; near death within 24h; and confirmed late-onset infection (including validation of existing nosocomial sepsis predictive scores). At the end of the

Protocol #: 1

---

study a pre-post comparison of in-patient mortality incidence will be conducted as part of the process evaluation. This will use published mortality data from the pre-study period  and prospectively collected mortality data during the study period.

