## 6. Analysis of outcomes

### 6.1 Outcome definitions

Primary outcome:

All-cause mortality at 28d

Secondary outcomes:

1. Time from intervention/control procedures starting to death (days & hrs)
2. Mean cardio-respiratory stability at 24h of intervention (aSCRIP score)
3. Prevalence of hypothermia ( $T < 36.5^{\circ}\text{C}$ ) at 24h of intervention
4. Mean daily weight gain (g/day) at 28d
5. Proportion of infants exclusively breastfeeding at discharge
6. Mean duration of hospital admission (days & hours)
7. Incidence of clinically suspected infection after 3 days and by 28 days or latest follow up
8. Prevalence of neonatal intestinal carriage of ESBL-Klebsiella pneumoniae at 28d

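### New apnoea alone counts as suspected late-onset infection, while the SAP hypothesises a separate effect on apnoea; no planned analysis tells the two apart

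*SAP*

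**What the plan says.** - **Hypothesis.** SAP 2.2 describes "Early onset, late impact causal pathways, including prevention of late-onset infections, gastro-intestinal stability and prevention of apnoea of prematurity". Prevention of infection and prevention of apnoea of prematurity are separate items in that list. Protocol 1.2 words the apnoea pathway differently, as "improved recognition of apnoeic events needing resuscitation".
- **Outcome.** SAP 6.1 lists secondary outcome 7 as "Incidence of clinically suspected infection after 3 days and by 28 days or latest follow up" and does not define it further. Protocol 2.1 and SAP 2.3 both place late-onset infection under Objective 2 (clinical outcomes).
- **Definition.** The Protocol Definitions require "New onset of any 1 of the following at > 72h of age", and the signs are "Pallor; Lethargy; Jaundice; Apnoea; Hepatomegaly". No culture is needed for a suspected case. A confirmed case has the same signs "AND blood or CSF culture positive for known neonatal pathogen".
- **Narrowing of the apnoea sign.** Protocol 6.1.3, Figure 4 (criteria for taking cultures) has a footnote that limits apnoea to "Spontaneous apnoea with no identifiable reason". Its examples of identifiable reasons are milk aspiration, severe respiratory distress and end-stage respiratory failure.
- **Use of confirmed infection.** It is not among the eight secondary outcomes. Protocol 10.3 uses "confirmed late-onset infection (including validation of existing nosocomial sepsis predictive scores") only in a regression for risk factors.

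**The concern.** The plan expects the intervention to change apnoea by a route other than infection, and it counts apnoea as a sufficient sign of infection. If early contact reduced apnoea of prematurity and left infection unchanged, outcome 7 would fall, and the report would credit the intervention with preventing infection. If early contact mainly made apnoea more likely to be noticed, outcome 7 would rise and could hide a real infection benefit. What is at stake is the Objective 2 conclusion about late-onset infection, and any use of that conclusion to explain a mortality difference. The comparison of 28-day mortality is not touched.

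**Working it through.** **Step 1: can apnoea of prematurity make a case by itself?** The Definitions accept any one sign, so new apnoea after 72h is enough. The Figure 4 footnote would remove apnoea with an identifiable reason. However, its list is illustrative and does not mention apnoea of prematurity, and it is attached to the culture-taking criteria. The outcome definition does not carry it. Whether apnoea of prematurity counts is therefore unstated.

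**Step 2: does another planned analysis separate the two effects?**
- SAP 6.4.1 (cardio-respiratory stability) covers only the first 24h of participation.
- SAP 6.5 gives the number and proportion of babies with an SAE. Apnoea needing bag-valve-mask ventilation is one of several life-threatening events in Protocol 8.3, and the SAP does not ask for it by arm on its own.
- Confirmed infection is not compared between arms.
- SAP 6.2 has no breakdown of outcome 7 by sign.

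So none does.

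**Step 3: size.** The plan gives no figure for this point. The arm size comes from the sample-size statement: 48% against 0.70 × 48% = 33.6%, two-sided 0.05, 80% power. The continuity-corrected two-proportion formula gives 196 per arm, 392 in total, which matches the plan.

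Let f be the share of suspected cases that qualify by apnoea alone, and r the relative reduction in those cases. With no effect on infection:

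expected risk ratio = (1 − f) + f(1 − r) = 1 − f·r

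The documents give neither f nor r. Assumed ranges are f = 10% to 50% and r = 30% to 50%:

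| f | r = 30% | r = 50% |
|---|---|---|
| 10% | 0.97 | 0.95 |
| 30% | 0.91 | 0.85 |
| 50% | 0.85 | 0.75 |

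Babies with apnoea plus another sign still count, so they do not enter f.

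If better recognition instead raised apnoea-only cases by the same proportions, the sign reverses: 1 + f·r, from 1.03 to 1.25.

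**Step 4: chance of a significant result in favour of the intervention with no infection effect.** This is a two-proportion test at two-sided 0.05 with 196 per arm. Control incidence is also not in the documents and is assumed to be 20% to 50%.

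| Control incidence | f = 10%, r = 30% | f = 30%, r = 50% | f = 50%, r = 50% |
|---|---|---|---|
| 20% | 3.5% | 11.6% | 25.5% |
| 35% | 4.1% | 19.8% | 46.8% |
| 50% | 4.8% | 31.8% | 70.5% |

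Only results favouring the intervention are counted, for which the nominal rate is 2.5%. Twin clustering and babies who die before 72h are ignored.

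**The case against.** The strongest reply is that the plan does not hide the outcome's limits. It is labelled clinically suspected. Protocol 6.2.2 explains why a clinical score is used where laboratory markers are unavailable, and reports its sensitivity (77.1%) and PPV (64.9%) against culture. The onset must be new and after 72h, and Figure 4 also requires clinical deterioration. Nothing in the documents shows that apnoea brings in more non-infective cases than the other four signs. Differential recognition is limited because both arms have alarmed oximetry until stable, restarted after certain deteriorations (Protocol 8.1).

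Most of that stands, and it limits the size of the problem. It does not remove it. Accuracy against culture in another population does not protect a comparison between arms when the intervention is expected to change one of the signs directly.

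Three stronger readings are tempting, and the documents do not support them:

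- **That outcome 7 fails Objective 4.** Suspected infection is assigned to Objective 2. The infection-related measure listed under Objective 4 in Protocol 2.1 is ESBL-Klebsiella carriage, which does not involve apnoea.
- **That the footnote definitely keeps apnoea of prematurity.** Its list is of examples, and a clinician could treat prematurity as an identifiable reason. The supportable statement is that its classification is not given.
- **That the PPV sets the size.** Taking the culture-negative share (1 − 0.649 = 35.1%) as f and halving apnoea gives 1 − 0.35 × 0.5 = 0.825. At 40% control incidence, that gives significance in about 24% of trials with 147 per arm and 30% with 196. This needs every culture-negative case to be apnoea-only and uninfected, which the documents do not show.

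**Conclusion.** The overlap is real. As planned, a difference in outcome 7 cannot be attributed to infection rather than to a non-infective effect on recorded apnoea, and the documents name such effects in both directions. The size is unknown. Under the assumed ranges the risk ratio with no infection effect is 0.97 to 0.75. At the low end this is negligible. At the high end it could produce a significant result that says nothing about infection. The structural point needs none of these figures: it rests on the any-one-sign rule, the separate apnoea hypothesis and the absence of any analysis that splits them.

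The weight is minor to moderate, because one secondary outcome and its interpretation are affected. It is best treated as a cheap improvement.

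**What to change.** Add to SAP 6.2 before the database is closed:

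1. Report outcome 7 by qualifying sign and by arm, including the number of cases with apnoea as the only sign. State whether apnoea of prematurity counts, and whether the Figure 4 footnote applies to the outcome.
2. Pre-specify a sensitivity analysis of outcome 7, with the same model, that leaves out culture-negative episodes whose only qualifying sign is apnoea.
3. Report apnoea needing bag-valve-mask ventilation after 72h by arm, from the SAE records.

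Item 3 is limited to these events because complete capture of any apnoea is not shown. The daily review list in Protocol 6.1.2 has no apnoea item, reviews in the KMC unit are weekly, and oximetry generally stops once the baby is stable.

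The cost is a few lines, one table and one extra model run, using deterioration reviews, culture results and SAE reports the protocol already calls for. The sensitivity analysis has fewer episodes and leaves out some true culture-negative infections that present only with apnoea, so it should sit beside outcome 7 and not replace it. Outcome 7, the primary analysis and the sample size do not change.
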